In CENTAUR, the safety profile of CVC (150 mg QD) was comparable to that in participants treated with placebo and was well tolerated over 2 years. The types, severity, and frequency of TEAEs reported after 2 years of CVC treatment was consistent with those reported after 1 year of treatment. The overall incidence of TEAEs during the study was similar across the treatment groups ($\geq 95.0\%$ of participants in each group). No deaths occurred during the study. The frequency and types of TEAEs reported were comparable between treatment groups during Year 1 and Year 2.

- The frequency of treatment-related events reported after 2 years of CVC treatment was comparable to that reported after 1 year of treatment (41.7% vs 42.1%).
 - The most frequently reported drug-related TEAEs of at least Grade 2 severity through 1 year of treatment were fatigue (2.8%) and diarrhea (2.1%) in the CVC arm and headache (3.5%) in the placebo arms.
 - The most frequently reported study drug-related TEAEs of at least Grade 2 severity through 2 years of treatment were fatigue (5.0%) in the CVC/CVC group, headache

in the placebo/CVC group (6.6%), and ALT increased (3.3%) in the placebo/placebo group.

- For participants who crossed-over from placebo and received CVC for 1 year, the frequency of TEAEs reported (44.3%) was similar to that reported in participants who received 1 year CVC during Treatment Period 1 of the study (41.7%). A smaller number of participants experienced TEAEs that resulted in discontinuation of study drug.
- After 2 years of CVC treatment, the number of participants who discontinued the study due to a TEAE was greater than that reported for participants treated with 2 years of placebo (4.1% vs 0), but was comparable to that reported after 1 year of treatment (6.3%).
 - The only AE leading to discontinuation, regardless of causality, reported in at least 2 participants in the CVC/CVC group was ALT increased (3 participants, 2.5%); all were Grade 3 severity.
- Although the number of participants who experienced serious adverse events (SAEs) increased after 2 years of CVC treatment compared to placebo (18.2% vs 11.8%), almost all were considered not-related to study drug and did not lead to study discontinuation.
- Only 1 participant experienced a study drug-related event (Grade 3 heart arrhythmia), and only 1 event led to discontinuation (Grade 3 congestive heart failure considered not related to study medication).
- With the exception of treatment-emergent Grade 3 and 4 amylase elevations and Grade 4 lipase elevations observed more frequently in the CVC arms versus the placebo arm (3.3% versus 1.7%, 2.2% versus 0.0%, and 21.1% versus 16.7%, respectively), the incidence of treatment-emergent Grade 3 or 4 laboratory results were generally similar between the CVC arms and the placebo arm
- No meaningful changes in vital signs or anthropometric parameters were observed.
- Overall, the proportion of participants with confirmed liver transaminase elevations that met protocol-defined biochemical criteria for suspected drug-induced liver injury was 9.7% in the CVC group and 7.6% in the placebo group during the first year of treatment. The frequency did not increase in CVC-treated participants in Arm A after an additional year of treatment with CVC. No cases of Hy's law were observed in the study. Among the participants who met the criterion for suspected drug induced liver injury, 2 hepatobiliary adverse events of autoimmune hepatitis were reported during Year 1 (1 participant in the CVC Arm A and 1 participant in the placebo Arm C). These participants did not continue onto treatment during Year 2. In addition, a case of possible autoimmune hepatitis was observed upon liver biopsy (1 subject in CVC Arm A, event not reported as an AE or SAE by the investigator). No cases of autoimmune hepatitis were observed during Year 2 of the study.
- There have been no deaths related to CVC treatment.

Based on the results of CENTAUR, the Phase 3 AURORA study was initiated in April 2017 to study the antifibrotic benefit of CVC as compared with placebo in adults with NASH and Stage 2 or 3 fibrosis. CVC is currently also in Phase 2 development in subjects with primary sclerosing cholangitis (PSC).

In over 1000 subjects treated, including those with NASH and liver fibrosis, HIV-1 infection, and cirrhotics with hepatic impairment, CVC demonstrated good safety and tolerability (Abdelmalek M et al 2017, CVC IB), supporting evaluation in combination therapy with tropifexor for the treatment of liver fibrosis associated with NASH.

This study is the first study with a combination of tropifexor and CVC in patients with biopsy confirmed NASH and it aims to assess safety and tolerability as well as efficacy after daily dosing for 48 weeks.

Tropifexor and cenicriviroc (combination) pre-clinical data

A preclinical animal study investigating the potential additive effects of CVC and tropifexor in STAM mouse models of diet induced NASH, shows that combination therapy of tropifexor and CVC further improved steatosis, ballooning, and inflammation as measured by NAS vs. vehicle when compared to either agent as monotherapy (Laffitte B, AASLD 2017 abstract # P-2052). The combination of tropifexor and CVC was associated with more pronounced reductions in lobular inflammation and hepatocellular ballooning. Tropifexor, CVC, and the combination all reduced fibrosis to a similar extent vs. vehicle. These preclinical combination data supports further evaluation in humans.

Tropifexor and cenicriviroc (combination) toxicology data

In accordance to the International Conference on Harmonization (ICH) guidance on non-clinical safety studies (ICH) M3 (R2) section XVII (combination drug toxicity testing), 4 and 13 week GLP combination studies were performed in rats to support the long term clinical development of the 2 investigational drugs CVC and tropifexor as combination therapies for NASH.

CVC and/or LJN452 were administered separately or in combination, daily via oral gavage to rats for 28 days (Study 652-9-1059). The groups and doses were as indicated in the Table 1-1 below:

Table 1-1 Study design 28 day oral gavage combination study

Group	No. of Animals		CVC Dose Level	CVC Dose Concentration	LJN452 Dose Level	LJN452 Dose Concentration
	M	F	(mg/kg/day)	(mg/mL)	(mg/kg/day)	(mg/mL)
1 (Control)	10	10	0	0	0	0
2 (CVC low)	10	10	30	6.0	0	0
3 (CVC high)	10	10	100	20.0	0	0
4 (LJN452 low)	10	10	0	0	0.03	0.006
5 (LJN452 High)	10	10	0	0	1.0	0.2
6 (CVC+LJN452) (low)	10	10	30	6.0	0.03	0.006
7 (CVC+LJN452) (high)	10	10	30	6.0	1.0	0.2

Source: Study 652-9-1059

CVC = Cenicriviroc; F = Female; M = Male

Administration of CVC alone or in combination with LJN452 was generally well-tolerated when administered via oral gavage for 28 days. The only effects noted during in-life phase were slightly decreased mean body weight and body weight change for males administered 1.0 mg/kg/day LJN452, alone or with 30 mg/kg/day CVC and slightly decreased food consumption for males administered 1.0 mg/kg/day LJN452 with 30 mg/kg/day CVC.

Clinical pathology changes were seen primarily in animals administered LJN452 and consistent with the changes reported in previous studies with LJN452 and with the expected pharmacology of the drug. Most of the test-article related clinical chemistry effects may be associated with expected pharmacology of the test article(s).

Clinical pathology changes in animals administered CVC included minimally to mildly lower absolute monocyte counts which was attributed to the pharmacology of CVC (CCR2 antagonism) and was not noted in animals administered LJN452 alone.

Based on the microscopic findings, primary target tissues for LJN452 were the liver, kidney, and intestines as previously reported in other studies with LJN452 alone. These findings may be attributable to the pharmacologic activity of LJN452, as FXR is highly expressed in the liver, kidney, and intestines. Secondary findings, consistent with stress, were observed in the thymus and prostate in animals administered LJN452, which correlated with decreased individual and/or group thymus and prostate weights, respectively, as well as decreased individual terminal body weights.

In conclusion, administration of CVC alone caused no microscopic findings indicative of toxicity and administration of CVC in combination with of LJN452 had no impact on toxicity of LJN452.

CVC and LJN452 were administered in combination daily via oral gavage to rats for at least 13 weeks to assess the reversibility, persistence, or delayed occurrence of any effects after an 8-week recovery phase (Study 1984-T01-052).

The groups and doses are presented in the [Table 1-2](#) below:

Table 1-2 Study design 13 weeks oral gavage combination study

Group	Sub-group	No. of Animals		CVC Dose Level	CVC Dose Concentration	LJN452 Dose Level	LJN452 Dose Concentration
		M	F	(mg/kg/day)	(mg/mL)	(mg/kg/day)	(mg/mL)
1 (Control)	1 (Tox)	15	15	0	0	0	0
	2 (TK)	3	3				
2 (Low)	1 (Tox)	15	15	3	0.6	0.03	0.006
	2 (TK)	6	6				
3 (High)	1 (Tox)	15	15	30	6	0.5	0.1
	2 (TK)	6	6				

Source: Study 1984-T01-052

CVC = Cenicriviroc; F = Female; M = Male; Tox = Toxicity; TK = Toxicokinetic.

No LJN452 or CVC related effects on mortality, clinical observations, ophthalmic observations, functional observational battery (neurobehavioral observations, elicited behaviors, or open field observations) occurred.

During the dosing phase, males administered $\geq 3/0.03$ mg/kg/day (CVC/LJN452) gained slightly less weight compared to controls, while females gained more. Both effects reversed during the recovery phase.

Several relatively minor, CVC- and LJN452-related clinical pathology findings were observed at the terminal sacrifice in animals administered $\geq 3/0.03$ mg/kg/day CVC/LJN452. These findings were attributed to the pharmacologic activity of CVC (CCR2 antagonism/decreased monocytes) or LJN452 (FXR agonism); those changes were similar to the one observed with the single agents (see above).

At the terminal sacrifice, CVC- and LJN452-related microscopic findings occurred in the liver, kidney, intestine (cecum, duodenum, and ileum) and the spleen. In the liver, minimal to moderate hepatocyte hypertrophy and periportal vacuolation was observed microscopically in animals administered 30/0.5 mg/kg/day. Higher liver weights correlated with hepatocellular hypertrophy and hepatocyte vacuolation in animals administered 30/0.5 mg/kg/day, hepatocellular hypertrophy in females administered $\geq 3/0.03$ mg/kg/day. In the intestine, an increased incidence of crypt/gland ectasia was noted in the cecum, duodenum, and ileum of animals administered 30/0.5 mg/kg/day. In the kidney, a CVC and LJN452-related increased incidence of basophilic tubules was noted in the cortex of males administered 30/0.5 mg/kg/day. Higher spleen weights correlated with the microscopic finding of increased marginal zone size in animals administered 30/0.5 mg/kg/day; this change is consistent with the effect of a pharmacological inhibition of CCR2 by CVC in the spleen (Flaishon 2004 et al). At the recovery sacrifice, no CVC and LJN452-related microscopic findings were observed, indicating reversibility of the changes observed during the dosing phase. The NOAEL is 30/0.5 mg/kg/day CVC/ LJN452).

Overall, the toxicity findings observed during the single agent studies and the combination studies were similar. The changes in clinical pathology were either due to the CCR2 pharmacology (decreased monocytes) or FXR agonism and were similar in the combination studies compared to the single agent studies. The primary target organs observed microscopically were the liver, kidney and gastrointestinal tract and were similar in the combination studies compared to the single agent studies. The nature and the severity of the findings in these organs were also similar. In addition, minimal to mild increased marginal zone in the spleen was observed after 13 weeks of treatment at 30/0.5 mg/kg/day CVC/LJN452. Although the mechanism of action has not been determined, this change is consistent with a pharmacological inhibition of CCR2 in the spleen (Flaishon 2004 et al). The NOAEL in the 13 week study was the high dose of 30/0.5 mg/kg/day CVC/LJN452.

In conclusion, the findings in the 4- and 13- week combination therapies were aligned with the findings observed in similar studies with the single agents and/or with their expected pharmacology.

Clinical tropifexor and cenicriviroc – drug-drug interaction results

A single site, randomized, parallel 3-arm, double-blind, double-dummy drug-drug interaction

(DDI) study was conducted in healthy subjects (LJC242A2101).

[REDACTED]

[REDACTED]

[REDACTED]

[REDACTED]

[REDACTED]

In summary, single drug treatment of tropifexor or CVC at 60 µg or 150 mg respectively, and the combination therapy of the two drugs at the same doses, all administered once daily for 14 days, were safe and well tolerated in healthy volunteer subjects. The safety and tolerability of the combination treatment of CVC + tropifexor were comparable to those of each of the mono therapy treatment.

[REDACTED]

[REDACTED]

[REDACTED]

[REDACTED]

[REDACTED]

[REDACTED]

[REDACTED]

[REDACTED]

[REDACTED]

[REDACTED]

[REDACTED]

Day 14 AUC_{0-24h} and C_{max} values correspond to values at steady state.

In summary, the co-administration of tropifexor has no marked impact on the pharmacokinetic profile for CVC, but co-administration of CVC reduces the tropifexor exposure (both C_{max} and daily AUC) by about 35% at steady-state. In conclusion, available results from the DDI study support the investigation of the combination treatment of tropifexor

[REDACTED]

with CVC in clinical trials.

Tropifexor and cenicriviroc – clinical DDI and food

The tropifexor + CVC drug-drug interaction study CLJC242A2101 in healthy subjects suggested that co-administration of CVC reduces tropifexor exposure (both C_{max} and AUC 0-24h) by about 35%. No safety concerns were identified at the doses of 60 µg tropifexor alone, 150 mg CVC alone or their combination, administered once daily with a standard breakfast for 14 days. In addition, an across-study exploratory comparison indicated that tropifexor plasma exposure (both C_{max} and AUC) at 60 µg administered fasted (study CLJN452X2101) is similar to that at the same dose administered following a standard breakfast (study CLJC242A2101).

In summary, as compared to the fasted status, a high-fat meal increases tropifexor exposure but a standard meal appears not to. It is recommended that NASH patients, in this study, will be dosed following a standard meal without high fat (i.e. per AHA diet see [appendix 17](#)).

Tropifexor and cenicriviroc (combination) - safety considerations

In the DDI study (CLJC242A2101) the safety and tolerability of the combination treatment of tropifexor + CVC were found to be comparable to those of each of the mono therapy treatment. No additional particular safety considerations are expected for the combination of tropifexor and cenicriviroc, beyond those previously observed for each of the individual monotherapies (see [section 1.1](#) and [section 3.6](#) for risks). As both drugs may increase liver transaminases, there is a potential for an additive effect, thus close liver monitoring is included. Diarrhea has been identified as a non-serious adverse effect for cenicriviroc and is a possible (but unconfirmed) adverse effect of tropifexor from animal studies.

Tropifexor and cenicriviroc (combination) - rationale

Due to the multifactorial etiology of NAFLD/NASH and limited monotherapy results so far, the combination therapy of compounds with different mechanisms of actions may provide more effective therapy for NASH patients.

This study will combine the potent FXR agonist (anti-steatotic, anti-inflammatory and anti-fibrotic) tropifexor and the CCR2/5 inhibitor (anti-inflammatory and anti-fibrotic) cenicriviroc. The preclinical animal study STAM mouse models of diet induced NASH, shows that combination therapy of tropifexor and cenicriviroc have additive effects on steatosis, ballooning, and inflammation.

Both tropifexor and cenicriviroc as monotherapy are currently being evaluated in phase 2 and phase 3 clinical trials, respectively CLJN452A2202 (clinicalTrials.gov Identifier: NCT02855164) and AURORA (clinicalTrials.gov Identifier: NCT03028740), and to date have shown improvements on biomarkers and in case of cenicriviroc improvements in liver fibrosis in NASH patients.

In summary, these two drugs have different mechanisms of action (FXR and CCR2/5 inhibitor), and this multi target approach may lead to greater efficacy than monotherapy alone.

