6.5.4 Laboratory evaluations

Laboratory evaluations will be assessed as indicated in [Table 6-1](#).

A central laboratory will be used for analysis of all specimens collected. Details on the collections, shipment of samples and reporting of results by the central laboratory are provided to investigators in the laboratory manual.

Clinically notable laboratory findings are defined in [Section 13 \(Appendix 1\)](#).

[REDACTED]

One sample of serum will be frozen and stored. This sample will be used to repeat study lab tests when needed. It may also be used for additional testing.

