6.5.4.2 Clinical chemistry

The following will be measured as indicated in [Table 6-1](#):

Clinical chemistry: sodium, potassium, chloride, bicarbonate, calcium, phosphate, blood urea nitrogen (BUN)/urea, serum creatinine, uric acid, creatine kinase, total protein, [REDACTED], haptoglobin and HbA1c. The estimated glomerular filtration rate (eGFR) will be calculated using the MDRD formula based on the patient's age at the time of measurement, gender and race.

At screening visit 1, the following assessments will be included: HbA1c, ferritin, transferrin saturation, iron, and if not historically available also ANA, ASMA, and AMA.

Optional: If the investigator requires additional data to evaluate the current alcohol use of the patient at the screening visit, the carbohydrate deficient transferrin (CDT) test can be assessed using the central lab.

Liver tests: see [Section 6.4.2](#)

Coagulation: see [Section 6.4.3](#)

[REDACTED]

[REDACTED]

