### **2.5 Analysis of the primary objective**

#### **2.5.1 Primary endpoint**

The primary study objective is to evaluate the safety and tolerability of tropifexor + CVC in patients with NASH and fibrosis (stage 2 or 3 as per NASH CRN histological score, F2/F3) by monitoring adverse events, vital signs and laboratory values during treatment as compared to monotherapy with each of tropifexor and CVC. The related endpoints are (over treatment):

- occurrence of adverse events,
- occurrence of serious adverse events,
- occurrence of adverse events resulting in discontinuation of study treatment,

- occurrence of adverse events of special interest,
- changes in vital signs and laboratory values.

Only treatment emergent adverse events will be considered for the analysis, which are defined as those starting on or after first day of application of study treatment and before EOS visit or 30 days after EOT visit, whichever comes earlier.

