### 2.8.3 Laboratory data

The summary of safety laboratory evaluations will be presented for the groups of laboratory tests (e.g., hematology, clinical chemistry). Descriptive summary statistics for the change from baseline to each study visit will be presented. These descriptive summaries will be presented by test group, laboratory test, and treatment group. Change from baseline will only be summarized for patients with both baseline and post baseline values. Shift tables based on the normal laboratory ranges will be provided. For the shift tables, the normal laboratory ranges will be used to evaluate whether a particular laboratory test value was normal, low, or high for each visit value relative to whether or not the baseline value was normal, low, or high. These summaries will be presented by laboratory test category and treatment group.

The number and percentage of patients with new clinically notable laboratory results after baseline will be presented. Clinically notable laboratory results are listed in Section 5.3.1, for those parameters where ranges are available.

Safety laboratory parameters which are at the same time part of the efficacy analyses will be included in the safety tables as well.

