**Table 5-1**      **Notable criteria for other laboratory parameters**

Parameter	Threshold value	Unit
Albumin	<32	g/L
Hemoglobin	<70	g/L
Hemoglobin	>200	g/L
White blood cell count	<2.0	10  /L
White blood cell count	>35.0	10  /L
Platelets	<50	10  /L
Platelets	>1000	10  /L
Prothrombin Time INR	>4.0	
PT	>40.0	sec
APTT	>80.0	sec
Sodium	<120	mmol/L
Sodium	>160	mmol/L
Potassium	<3.0	mmol/L
Potassium	>6.0	mmol/L
Glucose	<2.2	mmol/L
Glucose	>27.8	mmol/L
Calcium	<1.50	mmol/L
Calcium	>3.00	mmol/L
Phosphate	<0.29	mmol/L
Creatinine	>177	μmol/L
Calculated eGFR	<60	mL/min

[figure not shown]

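### SAP Table 5-1 sets no notable limit for amylase or lipase, the Grade 3/4 laboratory exceptions reported for CVC, so severe elevations would not be counted by arm

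*Protocol*

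**What the plan says.** Protocol Section 1.1, on the clinical experience with CVC, singles out "treatment-emergent Grade 3 and 4 amylase elevations and Grade 4 lipase elevations observed more frequently in the CVC arms versus the placebo arm". The rates are given as "3.3% versus 1.7%, 2.2% versus 0.0%, and 21.1% versus 16.7%, respectively", that is, Grade 3 amylase, Grade 4 amylase and Grade 4 lipase, CVC against placebo. Apart from these, "the incidence of treatment-emergent Grade 3 or 4 laboratory results were generally similar between the CVC arms and the placebo arm".

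Arms B, C and D contain CVC 150 mg; arm A is tropifexor alone (Protocol 3.1).

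SAP 2.5.1 lists "changes in vital signs and laboratory values" among the primary endpoints, and SAP Table 2-1 analyses them by descriptive statistics at each visit. SAP 2.8.3 adds change-from-baseline summaries, shift tables against the normal range, and a count of patients with new clinically notable results. For that count, "Clinically notable laboratory results are listed in Section 5.3.1, for those parameters where ranges are available". Section 5.3.1 classifies liver and renal events separately and gives the remaining limits in Table 5-1, "Notable criteria for other laboratory parameters". The table has 21 criteria on 14 parameters. Amylase and lipase are not among them.

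The chemistry list in Protocol 6.5.4.2 includes "uric acid, creatine kinase, total protein", then a redaction. Neither enzyme appears in the part that can be read.

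**The concern.** The safety of the combination against each monotherapy is the primary question, and it is answered descriptively. What the tables are set up to count therefore determines what the report can say. The protocol documents a specific laboratory imbalance for one component, expressed as the proportion of patients reaching a severity grade. The SAP table that would give the corresponding proportion by arm omits both analytes.

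This is the first study of the combination in biopsy-confirmed NASH. A reader of the report would want to know whether severe pancreatic enzyme elevations are more frequent in the CVC arms than in arm A, and whether they are more frequent in the combination arms than on CVC alone. As specified, the laboratory tables would not give those counts.

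**Working it through.** The plan states no figure for this point, so there is none to reproduce. The check is a comparison of outputs, followed by arithmetic on the size of the signal.

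**Which outputs could show a severe amylase or lipase value, if assayed**

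| Output | Source | What it would show |
|---|---|---|
| Descriptive statistics by visit | SAP Table 2-1, 2.8.3 | Distribution and change from baseline by arm; no count of patients above a severity limit |
| Shift tables | SAP 2.8.3 | Low, normal or high; a value just above normal and a Grade 4 value share a cell |
| Count of new notable values | SAP 2.8.3, 5.3.1, Table 5-1 | Nothing, because there is no limit for either enzyme |
| Liver and renal event counts | SAP 2.8.1, 5.3.1; Protocol Appendices 2 and 3 | Other analytes |
| Adverse events | Protocol 7.1 | Only values with symptoms, judged clinically significant, or needing therapy; severity is mild, moderate or severe, not laboratory grade |
| Adverse events of special interest | SAP Table 2-1, 2.8.1 | Depends on risk documents that are not available here, including the CVC Investigator's Brochure |

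No visible laboratory output gives the measure reported in Section 1.1.

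**Is either enzyme measured?** This cannot be settled. The readable chemistry list names neither, but part of it is redacted. Glucose has limits in Table 5-1 and is also missing from the readable list, so absence from that list is not evidence that an analyte is unmeasured.

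**Size, assuming the Section 1.1 rates apply to 48 weeks here and arm A behaves like placebo**

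Inputs: the three pairs of rates above; 50 patients per arm (Protocol 3.1); 193 randomised (Protocol, Amendment 3), so about 193 × 3/4 ≈ 145 on CVC.

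- Expected Grade 4 lipase cases per 50: 0.211 × 50 = 10.6 on CVC; 0.167 × 50 = 8.4 at the placebo rate.
- Excess: 0.211 − 0.167 = 0.044, so 0.044 × 50 = 2.2 per arm and 0.044 × 145 = 6.4 over the CVC arms. The total over those arms, 0.211 × 145 = 30.6, is mostly background.
- Chance of at least one event in a CVC arm of 50, 1 − (1 − p)^50: Grade 3 amylase, 1 − 0.967^50 = 81%; Grade 4 amylase, 1 − 0.978^50 = 67%; Grade 4 lipase, 1 − 0.789^50 > 99.9%.
- Power for Grade 4 lipase, 50 against 50, two-sided 0.10, normal approximation. The pooled rate is 0.189. SE under no difference = √(0.189 × 0.811 × 2/50) = 0.0783. SE under the alternative = √(0.211 × 0.789/50 + 0.167 × 0.833/50) = 0.0782. Then (0.044 − 1.645 × 0.0783)/0.0782 = −1.08, giving 14%, or 15% if rejections in the wrong direction are included. About 980 per arm would be needed for 80%.

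**How firm the signal is.** Section 1.1 gives no denominators for these rates. If they were 180 and 60, which reproduce all the percentages (for lipase, 38/180 = 21.1% and 10/60 = 16.7%), Fisher's exact p for lipase is 0.58 and the 95% interval for the difference is −6.8 to +15.6 percentage points. With 145 and 144 it is −4.6 to +13.4; with 240 and 120, −4.0 to +12.8. All include zero.

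**The case against.** The strongest reply is that Table 5-1 feeds one secondary display. The primary laboratory variable is change from baseline, analysed by visit, and needs no threshold. A reader might infer from the missing rows that the primary laboratory comparison cannot show an amylase or lipase effect, or that such values would appear nowhere. The documents do not support that: for any assayed analyte, the by-visit summaries and shift tables would display it. Nor can one infer that the enzymes are unmeasured, given the redaction.

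The adverse event routes also carry some weight. The central laboratory flags out-of-range values for investigator review (Protocol Appendix 1), significant ones become adverse events, and the special-interest category in SAP Table 2-1 extends to events identified during this or other studies. These routes are filtered by judgement or rest on documents not available here, so they are not a count of laboratory values. They are not empty either.

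It would also be wrong to call these enzymes the only laboratory signal known for either drug. Protocol 1.1 and 3.6 describe transaminase increases, and the plan counts those through Table 14-1.

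Finally, the signal is weak and a new row would not reliably detect it. That is correct, but it does not justify omitting the row. The whole safety assessment is descriptive, and the same argument would remove most rows of the table.

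**Conclusion.** The point holds in a limited form. Table 5-1 sets no limit for the two enzymes that the protocol names as exceptions among Grade 3 and 4 results on CVC. If they are assayed, severe elevations would be visible only as part of by-visit distributions and undifferentiated high shifts, and partly as adverse events. They would not be counted by arm.

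The consequence is a gap in description; no inference fails. At the Section 1.1 rates the Grade 4 lipase excess is about 2 patients per 50, or about 6 over roughly 145 CVC patients, with about 14 to 15% power. This assumes that those rates carry over to 48 weeks in this population (Section 1.1 does not state the period they cover) and that tropifexor alone leaves both enzymes at the placebo rate. Any CVC effect would have to be read mainly against arm A, the one arm without CVC; an added effect of tropifexor would be read against arm B.

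Whether the enzymes are in the panel remains open. A creatine kinase limit is a matter of preference and not part of this point: creatine kinase is in the readable panel, and no excess is reported for it.

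**What to change.** Confirm whether amylase and lipase are in the central laboratory panel. If they are, add a row for each to SAP Table 5-1 and tabulate the counts by arm under SAP 2.8.3. The severity limits have to be written into the SAP, because those behind the Section 1.1 percentages are not in the documents; using those limits would keep the counts comparable with the reported rates. Label the counts as descriptive.

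If the enzymes are not in the panel, consider testing the stored serum, of which Protocol 6.5.4 says "It may also be used for additional testing". That section describes one sample and shows no storage schedule, so it may not cover every visit. Failing that, state in the study report that this signal was not assessed.

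The cost is two table rows and, only if the enzymes were not run, some assays on existing serum. No extra visit or blood draw is needed.
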